2 STUDY OBJECTIVES

2.1 Primary Objective

The primary objective of this study will be to evaluate the efficacy of Gerdoff[®], a preparation based on CS, HA and aluminium hydroxide, in improving the upper symptoms in combination with a PPI (omeprazole) compared to treatment with PPI monotherapy (omeprazole), during 6 weeks of treatment and during the following 12-week maintenance follow-up period. The evaluation will be performed by means of the Reflux Symptom Index (RSI) questionnaire validated in Italian language.

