6 CLINICAL INVESTIGATION PLAN

6.1 Overall Study Design

This will be a phase III, multicentre, prospective, randomised, open-label, two-parallel groups study, followed by a follow-up period.

[figure not shown]
The study plan included a 6-week treatment period, from visit V1 to visit V4, of first-diagnosis patients presenting upper symptoms related to diagnosis of GERD, in the presence/absence of typical symptoms. Patients will be randomised to receive an open-label treatment (in a 1:1 ratio) with Gerdoff®- omeprazole (PPI) (Group 1) or omeprazole (PPI) alone (Group 2). The first administration of investigational products started in the morning of the day following visit V1.

At visit V4, patients in Group 2 who will be treated with omeprazole (PPI) alone, and patients in Group 1 who will be treated with Gerdoff®- omeprazole (PPI) and will be classified as non-responder, completed the study and the most appropriate therapy to treat their symptoms will be prescribed by the investigator.

To assess the maintenance of the effects of treatment, at visit V4 (end of study visit), patients in Group 1 who will be treated with Gerdoff®- omeprazole (PPI) and will be classified as responders could continue with a 12-week follow-up period. During the follow-up period patients could be randomly assigned as open-label (in a 1:1 ratio) to treatment with Gerdoff® or to a control group, which will not receive any treatment. To safeguard the health and well-being of patients, and to keep under control the possible upper symptoms of GERD that could appear, all patients that continued in the follow-up period received omeprazole as rescue medication in a quantity adequate to cover the entire follow-up period. This therapy will be chosen by the study coordinator as it is the treatment commonly used in clinical practice for the treatment of all specific and non-specific symptoms of GERD. The investigator explained to patients that rescue omeprazole could be taken only if necessary and according to the indications given by the Investigator, at constant dosage, and that use will be to be recorded in the daily diary by indicating the reason for administration. The investigator had to report the data in the source documents and in the electronic case report forms (eCRF).

A schematic diagram of the study design follows (Figure 1):

Figure 1. Study diagram

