8.1 Sample Size Justification

Although a search in literature has not identified any published article for trials that used the same investigation design as that used in the present study, some recently published articles (9, 13-15) allowed to formulate a sample size calculation for the present investigation.

The calculation of the sample size will be based on the primary objective of the investigation, i.e. to assess the change of RSI questionnaire from baseline to 6 weeks of treatment in the two treatment arms, Gerdoff®- PPI and PPI alone, based on an hypothesis that the addition of Gerdoff® to PPI could improve the effect of disappearance and of rapidity of control of upper symptoms of GERD. Such effect will be evaluated as the mean change in RSI compared to baseline, taking into consideration the variable age, standard deviation (SD) and expected value after treatment with omeprazole.

The following assumptions will be made for the sample size calculation:

Difference between the two arms (delta): 3.6; SD of the difference: 5.

Based on these assumptions, for a comparison based on unpaired Student t test, at a power of 80% and a level of probability of 5% for a two-tailed test, 62 patients (31 in each treatment arm) will be to be included in the study. Estimating a drop-out rate of 20%, 78 patients (39 in each treatment arm) will be to be included in the study.

The software PS Power and Sample Size Calculations Version 3.0, January 2009, will be used for the sample size calculation.

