8.2 Populations for Analysis

All efficacy and safety analyses will be conducted on the Intent-to-Treat population (ITT), defined as all randomized patients in the first period of study (first 6 weeks) who took at least one study treatment dose.

In addition to the primary analysis carried out on the ITT population, some secondary sensitivity analyses will be carried-out in accordance with the criteria mentioned above. The sensitivity analyses will be implemented according to the following criteria:

- Considering that a minimum intake of study treatment will be required for the assessment of the efficacy of therapy on the primary objective, it will be considered that evaluable patients on the primary end-point had taken at least 95% of the total dosage in the 6-week treatment period, as foreseen in the study protocol. Patients who will not reach this target will be excluded from the primary analysis, but entered in the sensitivity analysis to confirm the efficacy of treatment with Gerdoff® in the improvement of the high symptoms.
- Patients who took not allowed rescue medication will be excluded from the sensitivity analysis on the primary end-point.
- Patients who took drugs that interfere with salivary secretion remained included in the sensitivity
 analyses by derogation from the study protocol, since during the data review meeting the
 clinicians considered as not significant the interference of these drugs on the response of the
 primary variable.
- Patients who had a worsening of the upper symptoms and required an additional therapy or a modification of the dosage of omeprazole taken compared to the protocol during the 6-week

treatment period, according to the Investigator's opinion, will be considered major violators but remained in the study until visit V4 and entered into the ITT efficacy analysis. Such patients will be considered as non-responders in the analysis of the follow-up phase.

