8.3.2 Secondary Performance Analyses

All secondary variables will be listed and presented with the most appropriate descriptive statistics.

Number and percentage of responder/non-responder patients at end of treatment (visit V4)

Patients who at the 6th week of treatment showed a reduction of at least 50% vs. the baseline and an

absolute value < 13 will be considered as responders. The Chi-square test with the correction of Yates or, if more appropriate, the Exact Fisher's test will be used to compare the distribution of the proportions of responders and non-responders in the two treatment groups. The patients responders in the group treated with Gerdoff® + PPI entered the follow-up period and continued in the observation according to the procedures provided by the study protocol;

Change of frequency of symptoms from baseline to end of treatment (visit V4) of frequency of symptoms, assessed using the Likert scale

The same analyses foreseen for the RSI questionnaire will be performed.

Use of rescue medication

In the first 6 weeks of treatment, the intake in each treatment group of the rescue medication, allowed or not allowed, will be calculated as the frequency of intake of the specific drug and the comparison between groups will be performed using the Fisher's exact test.

In the first 6 weeks of treatment, the comparison of the median dose of rescue medication in the two study groups will be performed by means of the non-parametric (distribution-free) test of the median. If a mean value of intake could also be calculated, the comparison between the two treatment groups will be performed using the Mann-Whitney U test.

Patient satisfaction of treatment

This evaluation will be expressed with a semi-quantitative ordinal scale: 0 = low, 1 = discrete, 2 = good, 3 = excellent). The frequencies of judgments will be compared between groups using the Chisquare Mantel-Haenszel test.

In the follow-up period, the efficacy data collected will be presented by treatment group using only the most appropriate descriptive statistics and consistent with the current numerosity of the sample.

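### Responders are randomised a second time to assess maintenance, but section 8.3.2 plans no between-arm estimate or interval from that randomisation

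*Combined protocol and SAP*

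**What the plan says.** Section 6.1 sets up a second randomisation among Group 1 patients classed as responders at V4: "During the follow-up period patients could be randomly assigned as open-label (in a 1:1 ratio) to treatment with Gerdoff® or to a control group". Its stated purpose is to assess whether the effect lasts. Section 2.1 includes the period in the primary objective ("during the following 12-week maintenance follow-up period"). Section 2.2 makes the number and percentage maintaining the effect at V6, relative to V4, a secondary objective.

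A responder (sections 1.3 and 8.3.2) has an RSI fall of at least 50% from baseline and a value below 13 at week 6.

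For the analysis, section 8.3.2 states: "In the follow-up period, the efficacy data collected will be presented by treatment group using only the most appropriate descriptive statistics". The sentence goes on to tie this choice to the sample size actually available. Section 8.3 lists descriptive statistics as n, mean, SD, median, minimum and maximum, or counts and percentages. It makes two-sided 95% CIs the default unless something else is specified, and the word 'only' in 8.3.2 reads as specifying something else. The tests named in 8.3.1 and 8.3.2 are tied to the 6-week comparison or the treatment-period questionnaires; none is assigned to the follow-up arms.

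Section 8.2 has a single analysis set, "defined as all randomized patients in the first period of study (first 6 weeks"), limited to patients who took at least one dose. Section 6.5.2 (Visit 6) says maintenance is judged from the RSI and Likert data and gives no numerical criterion.

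**The concern.** The second randomisation exists to answer the maintenance question, and the quantity it identifies is the difference between the two follow-up arms. The plan prints each arm's figures but not that difference or its uncertainty. With roughly ten patients per arm, two bare percentages can look like a large effect, or a reassuring absence of one, when the data are compatible with both.

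The framing of maintenance adds to this. Patients enter follow-up because their V4 score was low, and section 2.2 measures maintenance against that same score. Selection on a low value means the next value is higher on average even if nothing has changed, so either arm read alone tends to show some apparent loss of effect.

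**Working it through.** **1. The plan's own figure.** Section 8.1 gives "Difference between the two arms (delta): 3.6; SD of the difference: 5", "at a power of 80% and a level of probability of 5% for a two-tailed test". Per arm, n = 2 × (1.960 + 0.842)² × 5² / 3.6² = 2 × 7.85 × 25 / 12.96 = 30.3, so 31. This reproduces "62 patients (31 in each treatment arm) will be to be included in the study". With dropout, 62 / 0.80 = 77.5, so 78, which reproduces "Estimating a drop-out rate of 20%, 78 patients (39 in each treatment arm) will be to be included in the study". No size, effect or precision is stated for the follow-up.

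**2. Likely size of the follow-up.** The documents give no responder rate, so this is an assumption.
- 50% of 39 Group 1 patients is 19.5, or about 10 per arm.
- 50% of 31 is 15.5, or about 7 per arm.
- Across 30% to 70% responders of 31 to 39 patients, the range is about 4 to 13 per arm.

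**3. Precision for RSI, unadjusted.** SD 5 is borrowed from section 8.1. Half-width = t(0.975, 2m − 2) × 5 × √(2/m).

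| m per arm | Half-width (RSI points) |
|---|---|
| 4 | 8.7 |
| 7 | 5.8 |
| 10 | 2.101 × 5 × 0.447 = 4.7 |
| 13 | 4.0 |

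Power for a 3.6-point difference is 14% at 4 per arm and 42% at 13 per arm. If all 39 Group 1 patients responded (19 per arm), it would be 58%.

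**4. Precision for RSI, adjusted for V4.** In the simulation described in step 6, the residual SD of V6 given V4 is about 2.7 to 4.6.
- At 10 per arm (17 df): 2.11 × 2.7 × 0.447 = 2.6 up to 2.11 × 4.6 × 0.447 = 4.3.
- At 7 per arm (11 df): 2.20 × 2.7 × 0.535 = 3.2 up to 2.20 × 4.6 × 0.535 = 5.4.

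**5. Precision for a proportion.** Take 8/10 v 5/10 as an illustration. The Wilson limits are 0.490 to 0.943 and 0.237 to 0.763. The Newcombe limits for the difference of 0.30 are:
- lower: 0.30 − √[(0.80 − 0.490)² + (0.763 − 0.50)²] = 0.30 − 0.407 = −0.107
- upper: 0.30 + √[(0.943 − 0.80)² + (0.50 − 0.237)²] = 0.30 + 0.300 = 0.600

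**6. Selection on V4.** The simulation assumed:
- true baseline RSI normal with mean 23 and SD 5, and entry at an observed RSI of at least 20;
- a mean fall of 12 or 14 (SD 4.5) to V4, with true V4 floored at 0;
- independent measurement error of SD 2 to 3.5 at each visit;
- the protocol's responder rule, and no true change after V4.

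Responder rates were 43% to 57%. Mean RSI among responders rose by 0.5 to 1.6 points from V4 to V6.

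A closed form gives the same order of size: rise = (1 − ρ) × SD × φ(z_p) / p, where p is the responder share and ρ the V4–V6 correlation. At p = 0.5, ρ = 0.7 and SD 5, this is 0.3 × 5 × 0.399 / 0.5 = 1.2. Over p of 0.3 to 0.7 and ρ of 0.5 to 0.9, it runs from 0.2 to 2.9.

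A second simulation under different assumptions, with patients split at random after selection, gave a between-arm difference in this rise of 0.00 to 0.04 points in absolute value. That is zero within simulation error, so the drift cancels in the randomised contrast.

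**The case against.** The strongest reply is that the plan gives its reason: the follow-up will be small. That stands as a reason not to test, given 14% to 42% power for 3.6 points. It does not extend to the interval, which is how small numbers are made visible.

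A reader might infer that the second randomisation yields no randomised comparison at all. The documents do not support that. Results are shown by treatment group, with n, mean and SD or counts, so an unadjusted difference and interval can be worked out from the printed columns. What is missing is a pre-specified, V4-adjusted estimate with its interval.

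A reader might also infer that regression to the mean biases the comparison of the arms, or that V6 against V4 is the only follow-up contrast. Neither holds. The drift is equal in expectation in both arms, and section 6.5.3 also lists RSI change from baseline to other time points, Likert change from baseline to V6, and symptom presence at V6.

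In the same simulation, 14% to 27% of responders no longer met the responder rule at V6 by chance. It is tempting to conclude that the reported percentage maintained will be too low by that amount. That assumes maintenance means still meeting the responder rule, which the documents do not say.

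Nor does section 8.2 force a wrong denominator. Sections 6.1 and 6.5.1 confine follow-up to re-randomised responders, so the gap is an unnamed analysis set.

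Finally, section 8 refers to a final SAP version 1.1 in an annex that is not supplied as a separate text and might say more.

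**Conclusion.** The point holds as a low-cost improvement to a stated secondary analysis. The 6-week primary comparison is unaffected. The plan randomises to assess maintenance and pre-specifies neither an estimate nor an interval for that contrast.

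At an assumed 10 per arm, the 95% half-width for RSI is about 4.7 points unadjusted at SD 5, against a planning difference of 3.6. With V4 adjustment it is about 2.6 to 4.3, which falls below 3.6 only in the lower-error scenarios. All of these widen if fewer patients enter. The comparison can be estimated but not confirmed.

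The within-arm drift of about 0.5 to 1.6 points is secondary. It matters only if one arm's V4-to-V6 change is read by itself. The responder rate, error SDs and use of SD 5 in follow-up are assumptions; the direction of the drift does not depend on their exact values.

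**What to change.** In section 8.3.2, replace the restriction to descriptive statistics with wording to this effect:

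- For all patients randomised at V4, analysed as randomised, the between-arm difference in V6 RSI, adjusted for V4 RSI, will be reported with a 95% CI. It is exploratory and no hypothesis test is planned.
- Rescue omeprazole use will be tabulated by arm beside it. Because rescue is available in both arms, the difference will be read as including its effect.
- The between-arm difference in proportion maintained will be reported with a 95% CI once an RSI-based analysis definition of maintenance is stated. Early discontinuation counts as failure, in line with section 6.3.3.
- Within-arm change from V4 to V6 will not be interpreted by itself as maintenance or loss of effect.

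In section 8.2, name the set of patients randomised at V4.

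The cost is SAP wording, one definition and a few table rows. The intervals will be wide and may look less favourable than bare percentages.

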8.3.3 Safety Analyses

All safety data will be listed and tabulated by study treatment and visit.

Adverse events

Adverse events reported will be assigned to a Preferred Term (PT) and will be classified by primary System Organ Class (SOC) according to the MedDRA thesaurus. Adverse events will be presented in a listing by treatment group. Summary tables will be also produced on the frequencies of recorded events.

Changes in vital signs

Changes in vital signs will be presented both in an individual line listing and in summary tables by treatment group.

Changes in hematology and blood chemistry parameters

Changes clinically significant will be presented both in an individual line listing and in summary tables according to the study treatment.

